Appendix F Definition of Relapsed and Refractory Myeloma

Refractory Myeloma:

Refractory myeloma is defined as disease that is non-responsive (failure to achieve minimal response or develops PD while on therapy) while on primary or salvage therapy, or progresses within 60 days of last therapy. There are 2 categories of refractory myeloma.

- Relapsed and refractory myeloma: Relapsed and refractory myeloma is defined as disease that is non-responsive while on salvage therapy or progresses within 60 days of last therapy in patients who have achieved minimal response or better at some point previously to then progressing in their disease course.
- Primary refractory myeloma: refractory myeloma is defined as disease that is non-responsive in patients who have never achieved minimal response or better with any therapy. It includes patients who never achieve MR or better in whom there is no significant change in M protein and no evidence of clinical progression; as well as primary refractory, progressive disease where patients meet criteria for true progressive disease.

Relapsed myeloma

Relapsed myeloma is defined as previously treated myeloma which progresses and requires the initiation of salvage therapy but does not meet the criteria for either primary refractory myeloma or relapsed and refractory myeloma.

(Adapted from Rajkumar SV, Harousseau J-L, et al. Consensus recommendations for the uniform reporting of clinical trials: report of the International Myeloma Workshop Consensus Panel 1. *Blood*. 2011;117[18]:4691-95) (25).

Appendix G Infusion Associated Reactions Observed with Isatuximab

Main types of infusion associated reactions

- Anaphylactic reaction
- Cytokine release syndrome
- Drug hypersensitivity
- Infusion related reaction

Symptoms typically associated with infusion reactions

- | | |
|--------------------------|-------------------------|
| • Abdominal pain | • Lacrimation increased |
| • Apnea | • Laryngospasm |
| • Bronchospasm | • Myalgia |
| • Chest discomfort | • Nasal congestion |
| • Chest tightness | • Nausea |
| • Chills | • Pruritus |
| • Cough | • Pyrexia |
| • Dizziness | • Respiratory distress |
| • Dysgeusia | • Rhinitis |
| • Dyspnea | • Rhinorrhea |
| • Feeling hot | • Stridor |
| • Flushing | • Tachycardia |
| • Headache | • Throat irritation |
| • Head discomfort | • Tracheal stenosis |
| • Hoarseness | • Tremor |
| • Hot flush | • Urticaria |
| • Hypertensive crisis | • Vision blurred |
| • Hypoxia | • Vomiting |
| • Influenza like illness | • Wheezing |
| • Injection site pain | |
-

Appendix H EORTC-QLQ-C30 scales, items and CIDs

ENGLISH

EORTC QLQ-C30 (version 3)

We are interested in some things about you and your health. Please answer all of the questions yourself by circling the number that best applies to you. There are no "right" or "wrong" answers. The information that you provide will remain strictly confidential.

Please fill in your initials:

--	--	--	--	--

Your birthdate (Day, Month, Year):

--	--	--	--	--	--	--	--	--	--

Today's date (Day, Month, Year):

31

--	--	--	--	--	--	--	--	--	--

	Not at All	A Little	Quite a Bit	Very Much
1. Do you have any trouble doing strenuous activities, like carrying a heavy shopping bag or a suitcase?	1	2	3	4
2. Do you have any trouble taking a long walk?	1	2	3	4
3. Do you have any trouble taking a short walk outside of the house?	1	2	3	4
4. Do you need to stay in bed or a chair during the day?	1	2	3	4
5. Do you need help with eating, dressing, washing yourself or using the toilet?	1	2	3	4

During the past week:

	Not at All	A Little	Quite a Bit	Very Much
6. Were you limited in doing either your work or other daily activities?	1	2	3	4
7. Were you limited in pursuing your hobbies or other leisure time activities?	1	2	3	4
8. Were you short of breath?	1	2	3	4
9. Have you had pain?	1	2	3	4
10. Did you need to rest?	1	2	3	4
11. Have you had trouble sleeping?	1	2	3	4
12. Have you felt weak?	1	2	3	4
13. Have you lacked appetite?	1	2	3	4
14. Have you felt nauseated?	1	2	3	4
15. Have you vomited?	1	2	3	4
16. Have you been constipated?	1	2	3	4

Please go on to the next page

During the past week:	Not at All	A Little	Quite a Bit	Very Much
17. Have you had diarrhea?	1	2	3	4
18. Were you tired?	1	2	3	4
19. Did pain interfere with your daily activities?	1	2	3	4
20. Have you had difficulty in concentrating on things, like reading a newspaper or watching television?	1	2	3	4
21. Did you feel tense?	1	2	3	4
22. Did you worry?	1	2	3	4
23. Did you feel irritable?	1	2	3	4
24. Did you feel depressed?	1	2	3	4
25. Have you had difficulty remembering things?	1	2	3	4
26. Has your physical condition or medical treatment interfered with your family life?	1	2	3	4
27. Has your physical condition or medical treatment interfered with your social activities?	1	2	3	4
28. Has your physical condition or medical treatment caused you financial difficulties?	1	2	3	4

For the following questions please circle the number between 1 and 7 that best applies to you

29. How would you rate your overall health during the past week?

1 2 3 4 5 6 7

Very poor Excellent

30. How would you rate your overall quality of life during the past week?

1 2 3 4 5 6 7

Very poor Excellent

Scale/subscale/item (abbreviation)	No. Items	Item Nos	CID ^a 95%CI	Reference
1. Global health status/HRQL (QL 2)	2	29 and 30	Improved ≥ 7 Deteriorated ≥ -7	Delforge 2015 Delforge 2015
Functional scales				
2. Physical functioning (PF)	5	1 to 5	Improved ≥ 9 Deteriorated ≥ -9	Dimopoulos 2012 Delforge 2015
3. Role functioning (RF)	2	6 and 7	Improved ≥ 15.8 Deteriorated ≥ -13.5	Bedard 2014 Bedard 2014
4. Emotional functioning (EF)	4	21 to 24	Improved ≥ 14.7 Deteriorated ≥ -12.2	Bedard 2014 Bedard 2014
5. Cognitive functioning (CF)	2	20 and 25	Improved ≥ 9.1 Deteriorated ≥ -3	Bedard 2014 Bedard 2014
6. Social functioning (CF)	2	26 and 27	Improved ≥ 5.3 Deteriorated ≥ 11.1	Bedard 2014 Bedard 2014

CID: clinically important difference

RF, EF, CF and SF CIDs from Bedard 2014 while QL2 and PF CIDs from Delforge 2015

a In addition, CIDs to be empirically derived from dataset using anchor-based methodology (calculate CID using performance status as an anchor (if performance status determined to be a reasonable anchor), examine the magnitude of change in the MY-20 patients who changed "meaningfully" on performance status. Best to have more than one anchor; and anchor(s) should be at least moderately correlated with the MY-20 to be considered useful (Cocks 2007, Revicki 2008, Wright 2012). Calculation of CIDs as mean score changes or by ROC analysis suggested that a change in the EORTC QLQ-C30 score in the range of approximately 6–17 is considered important by patients with MM, for patients with MM, the CIDs are closer to a medium ES than a small ES. Mean score changes smaller than 6 are unlikely to be important to the patients, even if these changes are statistically significant (Kvam 2010)

Scale/subscale/item (abbreviation)	No. Items	Item Nos	CID^a 95%CI
Fatigue (FA)	3	10, 12, 18	Improved \geq -10 Deteriorated \geq 10
Nausea and vomiting (NV)	2	14, 15	Improved \geq -10.2 Deteriorated \geq 1.9
Pain (PA)	2	9, 19	Improved \geq -12 Deteriorated \geq 12
Dyspnea (DY)	1	8	Improved \geq 12.7 Deteriorated \geq 5.6
Insomnia (SL)	1	11	Improved \geq -3.7 Deteriorated \geq 8.5
Appetite loss (AP)	1	13	Improved \geq -12.2 Deteriorated \geq 9.7
Constipation (CO)	1	16	Improved \geq -5.4 Deteriorated \geq 7.1
Diarrhea (DI)	1	17	Improved \geq 3.4 Deteriorated \geq 1.3
Financial difficulties (FI)	1	20	Improved \geq 9.8 Deteriorated \geq 2.7

CID: clinically important difference

a In addition, CIDs to be empirically derived from dataset using anchor-based methodology (calculate CID using performance status as an anchor (if performance status determined to be a reasonable anchor), examine the magnitude of change in the MY-20 patients who changed "meaningfully" on performance status. Best to have more than one anchor; and anchor(s) should be at least moderately correlated with the MY-20 to be considered useful (Cocks 2007, Revicki 2008, Wright 2012) Calculation of CIDs as mean score changes or by ROC analysis suggested that a change in the EORTC QLQ-C30 score in the range of approximately 6–17 is considered important by patients with MM, for patients with MM, the CIDs are closer to a medium ES than a small ES. Mean score changes smaller than 6 are unlikely to be important to the patients, even if these changes are statistically significant (Kvam 2010)

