--	--

[figure not shown]
	
known to be alive or the cut-off date, whichever is first. The final OS analysis (based on 220 deaths) is expected to be performed approximately 33 months after the final PFS analysis cut-off date (ie, 51 months after first patient in).
 
The analysis of DOR will be similar to that described for PFS. The same censoring rules as PFS will be used.
 
Analysis of PRO endpoints:
 
• Disease-specific HRQL (EORTC QLQ-C30) will be assessed via a comparison of C30 health-related quality-of-life change scores from baseline to EOT and 60 days after last study treatment administration between treatment arms. In addition responder analyses will be conducted: 1. for those who improve and 2 for those who deteriorate utilizing the clinical important differences (CID) defined in Appendix H for all C30 HRQL summary and subscale scores for both treatment arms.• Disease- and treatment-related symptoms (EORTC QLQ-C30 and MY20) will be assessed via a comparison of change scores in C30 (individual symptom change scores) and MY20 (disease- and treatment-related summary scores) from baseline to EOT and 60 days after last study treatment administration between treatment arms. In addition responder analyses will be conducted 1 for those who improve and 2 for those who deteriorate utilizing the CIDs defined in Appendix H for all individual symptom scores (C30) and disease- and treatment-related summary scores (MY20) for both treatment arms (Appendix I).• Health state utility (EQ-5D-5L) will be assessed via a comparison of health state utility change scores from baseline to EOT and 60 days after last study treatment administration between treatment arms. In addition responder analyses will be conducted 1 for those who improve and 2 for those who deteriorate utilizing the CIDs defined in Appendix J for health state utility scores for both treatment arms.• Health status (EQ-5D-5L Visual Analogue Scale) will be assessed via a comparison of EQ-5D-5L health status change scores from baseline to EOT and 60 days after last study treatment administration between treatment arms. In addition responder analyses will be conducted 1 for those who improve and 2 for those who deteriorate utilizing the CIDs defined in Appendix J for health status VAS scores for both treatment arms.• Clinically meaningful improvements for each PRO are defined (based on CIDs) in Appendix H, Appendix I and Appendix J. 
Analysis of the safety endpoints:
 
Number (%) of patients experiencing TEAEs by primary system organ class and preferred term will be summarized by CTCAE grade (all grades and \geq Grade 3) for the safety population. The same summaries will be prepared for drug-related TEAEs, TEAEs leading to treatment discontinuation, TEAEs leading to dose modification, serious TEAEs and TEAEs with fatal outcome. For patients with multiple occurrences of the same AE within the on-treatment period, the worst grade will be used.

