9.3.3.1 EORTC QLQ-C30

The EORTC QLQ-C30 is a cancer-specific instrument that contains 30 items and provides a multi-dimensional assessment of HRQL (17, 18, 19). The validity and reliability of the EORTC QLQ-C30 has been established in various types of cancers (20).

The EORTC QLQ-C30 provides a comprehensive assessment of the principal HRQL dimensions identified as relevant by cancer patients (physical functioning, emotional functioning, cognitive functioning, role functioning, social functioning, global HRQL, impact of symptoms and of toxicities). EORTC QLQ-C30 is one of the standard instruments used in oncology for the evaluation of new cancer therapies.

The QLQ-C30 is composed of both multi-item scales and single-item measures. These include five functional scales (physical, role, emotional, cognitive, and social functioning), three symptom scales (fatigue, nausea and vomiting, and pain), a Global Health Status (GHS)/quality of life scale, and 6 single items (dyspnea, insomnia, appetite loss, constipation, diarrhea, and financial difficulties). All of the scales and single-item measures range in score from 0 to 100. A higher score for a functional scale/GHS represents a higher/healthy level of functioning/HRQL, where a higher score for symptoms/items represents a higher level of symptomatology/problems. The recall period for this instrument is 1 week.

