11.4.6 Analyses of patient reported outcomes (HRQL/health economics) variables

Change from baseline for the following variables from EORTC QLQ-C30: global HRQL, five functional scales (physical, emotional, cognitive, role and social) and nine symptom domains (fatigue, nausea/vomiting, pain, dyspnea, insomnia, appetite loss, constipation, diarrhea, and financial difficulties); for the MY-20: future perspective, body image, disease symptoms and side effects of treatment; and for the EQ-5D-5L: health state utility value and VAS scores will be analyzed with an MMRM approach. Descriptive statistics including number of patients, mean and standard error will be provided. In addition, LS means, difference in LS means, the corresponding 95% CI's and the p-values will be provided for comparison between treatment arms.

Responder analyses will also be conducted using established MIDs (to be described in SAP) for each of the above variables.

Each of the following criteria will be assessed via a comparison of change scores from baseline to EOT and 60 days after last study treatment administration between treatment arms:

- A) Disease-specific HRQL (EORTC QLQ-C30)

- B) Disease- and treatment-related symptoms (EORTC QLQ-C30 and MY20)
- C) Health state utility (EQ-5D-5L)
- D) Health status (EQ-5D-5L visual analogue scale).

In addition, responder analyses will be conducted:

1. For those who improve.
2. For those who deteriorate.
3. For those who stay the same.
4. Time to definitive improvement, and time to definitive deterioration will be based using the CIDs defined in [Appendix H](#), [Appendix I](#), and [Appendix J](#).
5. Deterioration will be considered definitive if no later improvement above the defined thresholds (CIDs defined in [Appendix H](#), [Appendix I](#), and [Appendix J](#)) are observed, prior to further anticancer therapy.
6. Improvement will be considered definitive if no later deterioration above the defined thresholds (CIDs defined in [Appendix H](#), [Appendix I](#), and [Appendix J](#)) are observed, prior to further anticancer therapy.

Full details will be provided in the SAP.

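### Protocol Appendix H gives 4 of the 15 QLQ-C30 rows two positive cut-offs, so one responder category in each of those rows points the wrong way

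*Protocol*

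**What the plan says.** Protocol 9.3.3.1 fixes the direction of scoring: a higher score is better on the functional and global scales, and for symptoms it is the reverse, "where a higher score for symptoms/items represents a higher level of symptomatology/problems".

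Protocol Appendix H then gives an improved and a deteriorated cut-off for each of 15 rows. In 11 rows the two cut-offs have opposite signs that agree with this direction; fatigue, for example, is "Improved \geq -10 Deteriorated \geq 10". In four rows both are positive:

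- Dyspnea: "Improved \geq 12.7 Deteriorated \geq 5.6"
- Diarrhea: "Improved \geq 3.4 Deteriorated \geq 1.3"
- Financial difficulties: "Improved \geq 9.8 Deteriorated \geq 2.7"
- Social functioning: "Improved ≥ 5.3 Deteriorated ≥ 11.1"

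The protocol summary plans responder analyses "utilizing the CIDs defined in Appendix H for all individual symptom scores (C30") and for the functional scales. Protocol 11.4.6 adds time to definitive improvement and to definitive deterioration, each cancelled by a later change the other way: "Deterioration will be considered definitive if no later improvement above the defined thresholds". That section also refers the responder thresholds to the SAP. The SAP prints none; section 2.4.9 plans descriptive change scores and leaves responder analyses to a possible separate document. A footnote to Appendix H plans empirically derived cut-offs in addition to the printed ones.

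**The concern.** A responder rule must assign a change score to at most one of improved and deteriorated, and to the correct one. With two positive cut-offs it does neither. A programmer following Appendix H would report worse dyspnea, diarrhea or financial difficulty as improvement, and better social functioning as deterioration. Genuine improvement on the three symptom items, and genuine worsening on social functioning, would not be counted at all. Protocol 11.4.6 also plans a group that stays the same. If that group means meeting neither cut-off, these patients would fall into it.

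Appendix H is the only rule for these rows in the two documents, so nothing elsewhere corrects it. The primary and key secondary endpoints are not touched.

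**Working it through.** **Reading used.** A positive cut-off means a rise of at least that size and a negative one a fall of at least that size. This is the only reading under which the signs in the other 11 rows make sense.

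**Score levels (SAP Appendix F).**

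- Single item: score = (Q − 1)/3 × 100, which gives 0, 33.3, 66.7 and 100. There are 4 × 4 = 16 baseline-to-visit pairs, of which 4 are unchanged, 6 rise and 6 fall.
- Social functioning, two items: score = (1 − (RS − 1)/3) × 100, with RS the mean of the two items. This gives 7 levels in steps of 16.7, so 7 × 7 = 49 pairs, of which 7 are unchanged, 21 rise and 21 fall.

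Every cut-off in the four rows is smaller than one step (at most 12.7 against 33.3, and at most 11.1 against 16.7). Only the sign decides the classification.

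**Single change, worked.** Dyspnea item 2 to 3: 66.7 − 33.3 = +33.3, a worsening. It is ≥ 12.7 (improved) and ≥ 5.6 (deteriorated). Dyspnea item 4 to 1: 0 − 100 = −100, the largest possible improvement. It meets neither. Social functioning up one step: +16.7, an improvement. It is ≥ 5.3 (improved) and ≥ 11.1 (deteriorated). Down one step: −16.7 meets neither.

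**All changed pairs, printed rule against the direction-correct rule with the same magnitudes.**

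| Row | Meets both | Meets neither | Improved wrong | Deteriorated wrong |
|---|---|---|---|---|
| Dyspnea, diarrhea, financial difficulties (each) | 6 of 6 worsenings | 6 of 6 improvements | 12 of 12 | 0 of 12 |
| Social functioning | 21 of 21 improvements | 21 of 21 worsenings | 0 of 42 | 42 of 42 |

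In the other 11 rows no change score meets both definitions and no category points the wrong way.

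**Definitive change, dyspnea, three post-baseline visits.** Assumptions: change is measured from baseline, and a change at the last visit stands because no later visit contradicts it.

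- Worse at all three visits. Correct: definitive deterioration at visit 1. Printed: visits 2 and 3 also count as improved and cancel the earlier dates, so deterioration is dated to visit 3. By the same logic the patient also meets definitive improvement at visit 3.
- Worse at visit 1, better than baseline at visits 2 and 3. Correct: no definitive deterioration. Printed: the later improvements are not recognised, so definitive deterioration is dated to visit 1.
- Better at all three visits. Correct: definitive improvement at visit 1. Printed: never.

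**Other slips in the same rows.** Financial difficulties is listed as item 20, but the questionnaire in Appendix H and SAP Appendix F use item 28. Social functioning carries the abbreviation CF, which belongs to cognitive functioning.

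**The case against.** The strongest objection is that the count of 4 depends on how the table is read. Every row uses ≥, including before negative numbers. Applied literally, that makes one category wrong in all 15 rows: fatigue improved, at ≥ −10, would be met by every worsening and missed by every improvement. If instead the label gives the direction and the number only the size, no row fails. The first point is correct but does not help the four rows. In the other 11 the sign recovers the intended direction; in these four it contradicts the score direction. The second reading would make the minus signs in those 11 rows redundant. A programmer who adopted it would, however, have classified patients correctly, provided the magnitudes are right.

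It can also be said that the table is visibly clerical and that a patient who is both improved and deteriorated would prompt a query. That is likely, but it leaves the rule to whoever resolves the query. A minus sign lost in reading the PDF cannot be excluded outright, but minus signs survive in all 11 other rows.

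The points on impact stand. Time to definitive change does not appear in the SAP. The separate patient-reported-outcome document, if it exists, may hold a correct table. SAP Table 10 schedules quality of life at the primary PFS analysis only, and SAP Table 1 shows that this analysis has been done. The pair counts are cells of a score grid, not expected numbers of patients.

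**Conclusion.** The concern holds. Four of 15 rows have one category in the wrong direction: improved for dyspnea, diarrhea and financial difficulties, and deteriorated for social functioning. At a single visit that category is wrong for every possible changed pair and the other is right. For time to definitive change both endpoints are affected.

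This rests on taking the printed sign as the direction of change; the definitive-change examples also assume change from baseline. The documents do not show whether only the signs are wrong or the values too, because the cited source is not part of them. The consequence is limited to secondary patient-reported outputs and becomes real only if responder analyses were or will be run from the printed table. It should be corrected, but it does not threaten the trial's main conclusions.

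**What to change.** 1. Check the signs and the values of the four rows against the study that Appendix H cites for them, on minimal important differences in advanced cancer.
2. Restate the table with direction-specific inequalities. Global and functional scales: improved if change ≥ +CID, deteriorated if change ≤ −CID. Symptom scales and items: improved if change ≤ −CID, deteriorated if change ≥ +CID. Improvement in dyspnea, diarrhea and financial difficulties, and deterioration in social functioning, then carry negative cut-offs. In the other 11 rows replace ≥ −x by ≤ −x.
3. Correct the financial-difficulties item from 20 to 28 and the social-functioning abbreviation from CF to SF.
4. Put the corrected table in the SAP or in the separate patient-reported-outcome document, wherever the responder analyses are specified.
5. Establish which rule was programmed in any responder or definitive-change output already produced. If the printed signs were used, annotate or rerun it.

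The cost is a source check, a one-page table and a programming check. No new data are needed.

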Appendix I MY20 scales, items and CIDs

ENGLISH

EORTC QLQ – MY20

Patients sometimes report that they have the following symptoms or problems. Please indicate the extent to which you have experienced these symptoms or problems during the past week. Please answer by circling the number that best applies to you.

During the past week:	Not at All	A Little	Quite a Bit	Very Much
31. Have you had bone aches or pain?	1	2	3	4
32. Have you had pain in your back?	1	2	3	4
33. Have you had pain in your hip?	1	2	3	4
34. Have you had pain in your arm or shoulder?	1	2	3	4
35. Have you had pain in your chest?	1	2	3	4
36. If you had pain did it increase with activity?	1	2	3	4
37. Did you feel drowsy?	1	2	3	4
38. Did you feel thirsty?	1	2	3	4
39. Have you felt ill?	1	2	3	4
40. Have you had a dry mouth?	1	2	3	4
41. Have you lost any hair?	1	2	3	4
42. Answer this question only if you lost any hair: Were you upset by the loss of your hair?	1	2	3	4
43. Did you have tingling hands or feet?	1	2	3	4
44. Did you feel restless or agitated?	1	2	3	4
45. Have you had acid indigestion or heartburn?	1	2	3	4
46. Have you had burning or sore eyes?	1	2	3	4

Please turn to next page

ENGLISH

During the past week:	Not at All	A Little	Quite a Bit	Very Much
47. Have you felt physically less attractive as a result of your disease or treatment?	1	2	3	4
48. Have you been thinking about your illness?	1	2	3	4
49. Have you been worried about dying?	1	2	3	4
50. Have you worried about your health in the future?	1	2	3	4

© Copyright 1999 EORTC Study Group on Quality of Life. All rights reserved.

Functional scales (abbreviations)	No. Items	Item Nos	CID^a
Future perspective (MYFP)	3	18 to 20	TBD
Body image (MYBI)	1	17	TBD
Symptom scales (abbreviations)			
Disease symptoms (MYDS)	6	1 to 6	-10 ^b
Side effects of treatment (MYSE)	10	7 to 16	-6 ^b

CID: clinically important difference

- a CID to be empirically derived from dataset using anchor-based methodology (calculate CID using performance status as an anchor (if performance status determined to be a reasonable anchor), examine the magnitude of change in the MY-20 patients who changed "meaningfully" on performance status. Best to have more than one anchor; and anchor(s) should be at least moderately correlated with the MY-20 to be considered useful (Cocks 2007, Revicki 2008, Wright 2012). *CID unknown CID will be calculated using performance status (PS) (0, 1, or 2 as compared to 3 or 4) as clinical outcome,
- b CID for improvement, Dimopoulos 2012

